6.4 Study Intervention Compliance

Medication adherence. There will be observed medication injection on day 10 and 40.

6.5 Concomitant Therapy

Concomitant medications will be recorded for the time period of one month before the initial screening visit throughout the follow up phase.

Prohibited medications include: benzodiazepines, barbiturates, antipsychotics, antidepressants, psychomotor stimulants (such as methylphenidate and amphetamine), antianxiety medications, naltrexone, disulfiram, modafinil, anticonvulsants, GABAergic drugs. Gabapentin prescribed for pain and not for a seizure disorder is acceptable.

Acceptable forms of birth control are:

- Oral contraceptives ("the pill")
- Contraceptive sponge,
- Barrier (diaphragm or condom),
- Intrauterine contraceptive system (Mirena®, Paragard®)
- Levonorgestrel implant (Norplant®)
- Etonogestrel implant (Implanon®)

- Medroxyprogesterone acetate contraceptive injection (Depo-Provera®)
- Complete abstinence from sexual intercourse
- Hormonal vaginal contraceptive ring (NuvaRing®)
- Patch (Ortho Evra®)
- Surgically sterile
- Partner surgically sterile

Additional psychosocial therapies including self-help groups will be allowed during the randomized medication phase but will be measured using the Treatment Services Review (TSR).

7 STUDY INTERVENTION DISCONTINUATION AND PARTICIPANT DISCONTINUATION/WITHDRAWAL

7.1 Discontinuation of Study Intervention

Stopping rules will be having SAEs or unexpected AEs attributable to study medication in 10% or more patients, or 3X as many SAEs or unexpected AEs in a single arm. Mild irritation at an injection site that resolves with treatment in 3-7 days will not be counted as an unexpected AE's; an infection that does not resolve in 7 days or progresses to an abscess that needs surgical intervention will be counted as an unexpected AE or SAE depending on the need for hospital treatment.

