3.4 Primary Safety Endpoints

Brixadi adverse events: **Brixadi** has been shown to be safe and well tolerated in a number of Phase I, II and III trials, involving approximately 120 subjects. The most common side effects of **Brixadi** noted in clinical trials include: Adverse reactions most frequently reported for buprenorphine are headache, nausea, hyperhidrosis, insomnia, drug withdrawal syndrome and pain. Uncommon (between 1 and 0.01%) adverse events reported include Infection, Influenza, Pharyngitis, Rhinitis, injection site cellulitis, Lymphadenopathy, Hypersensitivity and Decreased appetite.

There were no medication-related Serious Adverse Events in any of the clinical trials conducted thus far. . In the proposed trial, patients will be monitored remotely twice a week for adverse events and weekly in person by a nurse or trained research staff for presence of adverse events or clinical deterioration.

Clinical deterioration and/or suicide risk management: All of the investigators have had experience managing and referring subjects under these conditions. The TRC follows standing emergency policy when managing clinical deterioration related to addiction or psychiatric symptomatology for all of our subjects. At the weekly visit, subjects are evaluated for the presence or persistence of any symptoms, indicative of clinical deterioration due to a rapidly increasing problem with cocaine use, alcohol use, and/or psychiatric symptoms, including suicidality. Between visits, subjects are instructed to contact the study physician or an authorized research staff member in the event that disturbing symptoms become evident. In all cases, these subjects are immediately evaluated, and if deemed appropriate, are referred to clinical treatment. If possible, they will be maintained in the trial as long as it is deemed safe to do so. Also, any additional treatment is recorded for data analysis purposes. At any time, subjects who are severely suicidal or at high risk of medical or physical harm will be immediately discontinued from the trial and appropriate medical treatment instituted. All subjects who are discontinued from the trial are still encouraged to attend the follow-up visits.

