8.3 Adverse Events and Serious Adverse Events

8.3.1 *Definition of Adverse Events (AE)*

An **adverse event** (AE) is any symptom, sign, illness or experience that develops or worsens in severity during the course of the study. Intercurrent illnesses or injuries should be regarded as adverse events. Abnormal results of diagnostic procedures are considered to be adverse events if the abnormality:

- results in study withdrawal
- is associated with a serious adverse event
- is associated with clinical signs or symptoms
- leads to additional treatment or to further diagnostic tests
- is considered by the investigator to be of clinical significance

8.3.2 *Definition of Serious Adverse Events (SAE)*

Adverse events are classified as serious or non-serious. A **serious adverse event** is any AE that is:

- fatal
- life-threatening
- requires or prolongs hospital stay
- results in persistent or significant disability or incapacity
- a congenital anomaly or birth defect
- an important medical event

Important medical events are those that may not be immediately life threatening but are clearly of major clinical significance. They may jeopardize the subject and may require intervention to prevent one of the other serious outcomes noted above. For example, drug overdose or abuse, a seizure that did not result in in-patient hospitalization, or intensive treatment of bronchospasm in an emergency department would typically be considered serious.

All adverse events that do not meet any of the criteria for serious should be regarded as **non-serious adverse events**.

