10.1.2 Study Discontinuation and Closure

The study may be discontinued at any time by the IRB, the Sponsor, the FDA, or other government agencies as part of their duties to ensure that research subjects are protected.

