10.1.4 Safety Oversight

DATA AND SAFETY MONITORING:

10.1.5 *During the course of the study, data and safety monitoring will be performed on an ongoing basis by the Principal Investigator- [name], Medical Director & Regulatory Sponsor- [name], Study Physician- [name], research staff, and the site IRB. The PI [name] PhD will have overall responsibility for data analysis and management, as well as overall responsibility for safety and data monitoring on a day-to-day basis. The PI will be responsible for reporting the adverse events and serious adverse events. This study will be monitored according to the monitoring plan as noted in DSMP. The study physician will be available to review medical issues related to participation for each participant on an ongoing basis as outlined in this protocol. The internal monitoring will be conducted on site at Center for Studies of Addiction by the study coordinator appointed by the PI. The study coordinator is qualified by education, experienced and have completed training on GCP. See their certifications and qualifications in the e-regulatory binder for the study. The study coordinator will be responsible for collecting and recording all clinical data. This includes ensuring that all source documents exist for the data on the case report forms, ensuring all fields are completed appropriately, and all corrections are done according to GCP. Any inconsistencies/deviations will be documented. The study coordinator will perform regular chart reviews to verify data integrity. Quality Assurance and Quality Control*

This study will be monitored according to the monitoring plan as noted above. The investigator will allocate adequate time for such monitoring activities. The Principal Investigator will also ensure that the monitor or other compliance or quality assurance reviewer is given access to all the above noted study-related documents and study related facilities (e.g. pharmacy, diagnostic laboratory, etc.), and has adequate space to conduct the monitoring visit.

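### The threefold between-arm stopping limb in section 7.1 is a bare ratio with no minimum count and no rule for a zero comparator, so a handful of events can meet it by chance

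*Combined protocol and SAP*

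**What the plan says.** Section 7.1 introduces its criteria as stopping rules and gives two, joined by "or". The first is "SAEs or unexpected AEs attributable to study medication in 10% or more patients". The second is "3X as many SAEs or unexpected AEs in a single arm". The only counting instructions concern injection sites: "Mild irritation at an injection site that resolves with treatment in 3-7 days will not be counted as an unexpected AE's", while an infection that persists beyond a week or becomes an abscess needing surgery does count.

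Four other sections bear on how the second limb would work:

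- **8.3.2** defines serious events broadly. Its examples of important medical events begin "For example, drug overdose or abuse, a seizure that did not result in in-patient hospitalization".
- **10.1.4** says that "data and safety monitoring will be performed on an ongoing basis" and adds "This study will be monitored according to the monitoring plan as noted in DSMP". The DSMP is not among the documents supplied.
- **10.1.2** keeps a separate power to stop: "The study may be discontinued at any time by the IRB, the Sponsor, the FDA", or other government agencies.
- **3.4** says of Brixadi: "There were no medication-related Serious Adverse Events in any of the clinical trials conducted thus far".

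Sections 8.3, 9.4, 10.1.2 and 10.1.4 give no minimum count, per-arm denominator, zero rule or look schedule for the threefold limb.

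**The concern.** A ratio of two small counts is very unstable. At 3 events against 1, or 3 against none, the threefold condition is already met, although such splits are common between arms with the same risk. Because the limbs are joined by "or", the 10% criterion does not act as a floor for the ratio.

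Two things are at stake. Followed literally, the rule could stop a trial of two approved drugs on a few events that say little about relative safety. Or staff who see that a 3-to-1 split is weak evidence may set the rule aside, and it then protects nobody. It is also unclear whether the restriction to events attributable to study medication, attached to the first limb, carries over to the second. That decides how many events count, and so how often chance alone meets the rule.

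**Working it through.** The plan states no operating characteristic for this rule, so there is no plan figure to reproduce.

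**Inputs**

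- Rule, as naturally read: larger count ≥ 3 and larger count ≥ 3 × smaller count, zero allowed (section 7.1; the floor of 3 is the reading, not the text).
- Allocation 1:1, from the equal groups in section 9.2. An event falls in either arm with probability 0.5 if the arms are equally safe, and in the worse arm with probability 3/(3+1) = 0.75 under a true threefold rate.
- Total qualifying events N ~ Poisson(m). **The documents give no m.** I use 0.5, 1, 3, 5 and 10 over both arms.
- Checking after every event. This is compatible with the ongoing monitoring in 10.1.4 but is not specified, so I also give a single check at the end.
- Equal denominators, one event per patient, trigger in either arm counted.

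**Step 1: where equally safe arms first meet the rule**

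- 3-0 at event 3: 2 × 0.5³ = 0.250
- 3-1 at event 4, not via 3-0: 2 × 3 × 0.5⁴ = 0.375
- 6-2 at event 8, from 2-2: (6 × 0.5⁴) × (2 × 0.5⁴) = 0.375 × 0.125 = 0.0469
- 9-3 at event 12: 0.0117; 12-4 at event 16: 0.0040

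The cumulative chance is 0.25 by the third event, 0.625 by the fourth, 0.672 by the eighth and 0.689 by the twentieth.

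**Step 2: average over the number of events**

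P(ever met) = Σ P(first met at event n) × P(N ≥ n).

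- m = 3: 0.250 × 0.577 + 0.375 × 0.353 + 0.0469 × 0.012 = 0.277
- m = 5: 0.250 × 0.875 + 0.375 × 0.735 + 0.0469 × 0.133 = 0.501 (later terms below 0.001)
- m = 10: 0.250 × 0.997 + 0.375 × 0.990 + 0.0469 × 0.780 + 0.0117 × 0.303 + 0.0040 × 0.049 = 0.661
- m = 0.5: 0.250 × 0.0144 + 0.375 × 0.0018 = 0.004
- m = 1: 0.250 × 0.0803 + 0.375 × 0.0190 = 0.027

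**Step 3: vary the checking, the true rate and the floor**

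| Chance of meeting the rule | m = 3 | m = 5 | m = 10 |
|---|---|---|---|
| Equal arms, floor 3, every event | 28% | 50% | 66% |
| Equal arms, floor 3, one check at end | 22% | 28% | 16% |
| Threefold rate, floor 3, every event | 38% | 65% | 85% |
| Threefold rate, floor 3, one check at end | 34% | 52% | 56% |
| Equal arms, floor 4, every event | 9% | 24% | 43% |
| Threefold rate, floor 4, every event | 18% | 43% | 74% |
| Equal arms, floor 5, every event | 3% | 11% | 31% |
| Threefold rate, floor 5, every event | 7% | 27% | 66% |

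The threefold rows hold the total fixed. If tripling one arm's rate doubles the total (1 + 1 becomes 1 + 3), the comparison at floor 3 with continuous checking is 28% against 73% (total 3 rising to 6) and 50% against 85% (5 rising to 10).

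**Step 4: other readings of the ratio.** Counting only 3-0 and 3-1, with no later crossings, gives 28%, 49% and 62%. Requiring at least one event in the lower arm gives 19%, 43% and 65%. If 2-0 counts, the figures are 49%, 67% and 77%. If 1-0 counts, the first event always meets the rule.

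**The case against.** The strongest reply is that the percentages depend on things the documents do not say. Event totals are not given. Ongoing monitoring describes general oversight, not a between-arm test after each event, and a single check cuts the 10-event figure from 66% to 16%. The second limb can fairly be read as shorthand for the same attributable events as the first. Section 3.4 and the statement in 2.3.1 that overdose is unlikely during treatment then point to low counts, where chance triggers are rare. The DSMP may hold the missing terms. A sensitive rule errs toward caution, and investigators may prefer that.

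Most of this stands as a limit on size. It does not supply a minimum count or a zero rule, and section 7.1 is where the stopping rule is stated. Low counts are not assured either. Section 3.4 speaks only of Brixadi, 8.3.2 lists overdose or abuse as typically serious in a trial of opioid use disorder, and 8.3.3.2 lets a temporal link to the injection make an event related.

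Three stronger readings are tempting but unsupported:

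- **That 66%, or certainty at the first event, is the rule's false-stop rate.** These figures need assumed event totals, continuous checking and, for certainty, the reading that 1-0 counts. The text fixes none of these.
- **That the plan gives no action when the limb is met.** Section 7.1 calls these stopping rules under a heading about discontinuing the intervention, so the implied action is to stop. Preferring a pause is a design judgement.
- **That the trial has no look schedule or minimum count anywhere.** Only the supplied documents can be checked, and they point to a DSMP that is not among them.

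**Conclusion.** The concern holds in a limited form and merits consideration before the rule is used. As written, the threefold limb has no minimum count and no zero rule, yet is labelled a stopping rule. On the natural reading with continuous checking, equally safe arms would meet it about 28%, 50% and 66% of the time at 3, 5 and 10 expected events; the problem is smaller with one check at the end and nearly vanishes at 0.5 to 1 expected event.

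The rule is not uninformative, since a true threefold rate meets it more often at every total shown. But at 5 expected events the contrast is 50% against 65% with the total held fixed, or 50% against 85% if the total doubles, so a trigger alone is thin grounds for stopping. The result rests on assumed totals, 1:1 arms with equal denominators, one event per patient and assumed checking. Clustered events or unequal drop-out would change the figures. Whether attribution applies to the second limb is a point to clarify, not a demonstrated error.

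**What to change.** Rewrite the threefold clause in section 7.1 so that it:

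1. makes meeting the limb trigger a pause in enrolment and dosing and a safety review, not an automatic stop;
2. compares the proportion of treated patients with a qualifying event in each arm;
3. requires a small minimum in the higher arm, for example 4 patients, so that a zero in the other arm has a defined consequence;
4. says whether only events attributable to study medication count, and when the comparison is made.

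Align the wording with the DSMP.

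The drafting cost is one paragraph and a short calculation. The real cost is sensitivity. With continuous checking, a floor of 4 lowers chance triggers from 28%, 50% and 66% to 9%, 24% and 43%. Under a true threefold rate it also lowers triggering from 65% to 43% at 5 expected events and from 85% to 74% at 10. A floor of 5 cuts chance triggers further (3%, 11%, 31%) but leaves only 27% and 66% sensitivity at 5 and 10. The choice of floor is therefore a trade-off, and a small floor combined with a review suits the purpose better than a large one. Case-by-case review of serious events, individual withdrawal under 7.2 and the powers to stop in 10.1.2 mitigate the loss. Items 1 and 4 need no loss of sensitivity and are worth doing whatever floor is chosen.

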7.2 Participant Discontinuation/Withdrawal from the Study

Participants are free to withdraw from participation in the study at any time upon request.

An investigator may discontinue or withdraw a participant from the study for the following reasons:

- Pregnancy
- Significant study intervention non-compliance
- If any clinical adverse event (AE), laboratory abnormality, or other medical condition or situation occurs such that continued participation in the study would not be in the best interest of the participant
- If the participant meets an exclusion criterion (either newly developed or not previously recognized) that precludes further study participation
- Participant missing a due injection for more than 14 days.

The reason for participant discontinuation or withdrawal from the study will be recorded on the study Case Report Form (CRF) along with a note to file. Subjects who sign the informed consent form and are randomized but do not receive the injection may be replaced. Subjects

who sign the informed consent form and are randomized and receive the injection, and subsequently withdraw, or are withdrawn or discontinued from the study, will not be replaced.

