- 3) Participants who successfully complete detoxification, will undergo a neuroimaging session immediately followed by induction to XRNTX or XRBUP over a period of up to 14 days, which will include oral Naltrexone 50 mg for the XRNTX group followed by the 1st injection of XRNTX, or by injection of one or more weekly XRBUP in 8mg, 16mg or 24 mg strength with the total weekly dose not to exceed 32mg, followed by an injection of monthly XRBUP in 64, mg, 96mg, or 128mg strength (**Figure 1**). If deemed clinically necessary, induction to XRBUP may be extended by up to one week, using the same weekly Bixadi schedule. Buprenorphine/naloxone (Suboxone) is an FDA-approved sublingual form of buprenorphine that may be used during the induction if clinically indicated. Total duration of induction onto XRBUP will not exceed 14 days. Participants who are unable to complete the detoxification or induction will be excluded from the study and referred to a clinical addiction program for continuation of treatment as indicated. Suspected adverse reactions to any of the medications used in the study will be reported appropriately to the IRB, FDA at [name] or www.fda.gov/medwatch, Alkermes, plc at [name] or email: [contact] or both or Braeburn Inc at [name] .

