5.1 Inclusion Criteria

1. Males and Females
2. 18-65 Years old
3. OUD by DSM5 Criteria, confirmed by history and physical examination including urine toxicology, medical records and self-report
4. Opioids are the drug of choice
5. Interested in injectable extended release agonist or antagonist treatment
6. Have a stable address, working command of English language, and telephone access.
7. Women of childbearing age must use an effective contraceptive

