The clinical management of XRBUP is similar to XRNTX except that induction to XRBUP requires partial detoxification followed a weekly dose of injectable XRBUP, while induction on XRNTX requires complete abstinence (Lofwall et al 2018). The goal of the detoxification and induction phase of the experiment is to establish a uniform starting point for both monthly formulations. To achieve it, we will detoxify all participants to abstinence and randomize after abstinence from illicit opioids has been achieved. Outpatient detoxification to abstinence takes between 5 and 10 days. Following detoxification, the XRBUP participants will receive a combination of 8mg, 16mg, and 24mg strengths of weekly XRBUP, not to exceed 32 mg/week, followed by the injection of 64mg, 96mg, or 128mg of monthly XRBUP. If clinically indicated, supplemental doses of sublingual buropenorphine/naloxone (Suboxone) may be used. If clinically indicated, the induction procedure may be extended by up to one week, using the same approach. The total duration of induction to Brixadi will not exceed 14 days. The XRNTX participants will receive 50 mg of oral naltrexone for 7-10 days after detoxification followed by the 1st XRNTX (380 mg naltrexone IM) injection. The use of symptom-driven titration of weekly XRBUP during induction reflects current best practices in administration of the drug and increases participant safety and comfort. The XRBUP induction period is also intended to synchronize the timepoint at which both cohorts begin their monthly treatments. The non-opioid detoxification will follow the procedure described in our previous neuroimaging studies (Langleben et al 2014, Langleben 2015, Wang et al 2018). Participants who are opioid-positive upon screening will undergo office-based withdrawal management (detox) by the study physicians using FDA-approved generic medications to alleviate opioid withdrawal symptoms following a symptom-triggered approach that includes clonidine 0.1 mg tid, dicyclomine 20 mg qid, clonazepam 0.5 mg q12 hrs PRN, diphenhydramine 25 mg PRN, non-steroidal anti-inflammatory medicines PRN, Trazodone 50 mg qhs and oral hydration solutions (Molenberghs et al 2005). The induction to XRNTX or XRBUP will commence immediately after the baseline MRI session. The 1st monthly injection will be administered by an experienced nurse practitioner after induction is completed (approximately 7-14 days later).

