9 STATISTICAL CONSIDERATIONS

9.1 Statistical Hypotheses

Overview of primary hypotheses: Our primary response will be a binary indicator of treatment failure on the XRNTX or XRBUP regimen, defined as ≥ 2 weekly UDS positive for opioids, or self-report of ≥ 2 periods of three or more days of opioid use, or refusing XRNTX or XRBUP, or dropping out of study entirely. In hypotheses H1a and H1b, we are examining the effects of small, pre-specified, sets of measures, so our analyses will focus on model fit and prediction, and not on model selection. In hypothesis H1c, we search for best sets of predictors among demographic and clinical-behavioral variables, and over sets of brain/neural measures, so our focus is on model selection and on avoiding overfitting to the available data.

R61 Phase:

Hypothesis H1 (fMRI): For each of the cue reactivity (H1a), response inhibition (H1b), and connectivity (H1c) brain measured, we have a small number of neural responses associated with one or two regions of interest. These variables are continuously distributed, so we will test Hypotheses 1a, 1b and 1c using a repeated measures analysis of variance (rm-anova). The models will include a within-subject factor for Session (PRE vs ON) and a between-subject factor Group (XRNTX vs XRBUP), and their interaction. To accommodate the anticipated non-normal distributions of the response, we will use a generalized estimating equation (GEE) approach, using robust standard errors, using a compound symmetry working correlation structure for the within-subject correlations between the PRE and ON fMRI scans (Diggle PJ et al 2002). We will perform the rm-anova separately for each ROI (mPFC and VS for H1a, IFC for H1b, and VS-rtIFG and VS-mPFC for H1c). The hypotheses will be addressed by the Session by Group interaction, and we will obtain estimates and standard errors of the PRE vs ON change within each of the two groups, along with the size, standard error and significance of the differences between these estimates.

Sample size considerations for sample: The sample size is adequate for application of the GEE methods to obtain robust standard error (Lipsitz et al 1994). For a test of the PRE vs ON effect, our sample yields 80% power for a one-sided test that the ON levels will be Cohen's $d=0.4$ lower than the PRE levels, consistent with a decrease of Cohen's $d=0.5$ observed in our preliminary data and a decrease of Cohen's $d=0.3$ in the Suboxone sample.

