13 APPENDIX

13.1 Schedule of Activities (SoA)

	Screening detox and randomization (Day -14)	MRI Scan 1 Baseline (day 0)	Induction to XRBUP or XRNTX (day 0-10)	Injection 1 (day 10) + weekly follow up	Injection 2 (day 40)	MRI Scan 2 On Treatment (day 55)	Injection 3 (Day 70)	Weekly Follow- up End of study and referral (Day 100)
Psychiatric and medical								
Demographics (age ¹ , sex ¹ , edu ¹)		X						
History, physical and labs (C.4.a)		X						
SILS		X						
MINI (EOS* – end of study)		X						X EOS*
Addiction Severity Index ¹		X						X EOS*
Clinical/Behavioral (C.3.a)								
HAM-D ² , HAM-A ² , COWS ²	X	X	X		X	X		X
SOWS, Opioid Craving Scale ² , SF-MPQ-2 ² , STAI-6		X	X	X	X	X		X
TLFB interview	X	X	X		X	X		X
Ten-drug urine drug screen (UDS)	X	X	X	X	X	X		X
Go-NoGo errors of commission ²		X		X				
Neuroimaging (Section C.3.b)								
Go-NoGo fMRI ³		X			X			
Opioid Cue task fMRI ³		X			X			
Resting-state fMRI ³		X			X			
MPRAGE (anatomical MRI scan)		X			X			

PRINCIPAL INVESTIGATOR SIGNATURE

STUDY SPONSOR: [name]

STUDY TITLE: **Open label comparison of injectable extended release preparations of buprenorphine (Brixadi®) and naltrexone (Vivitrol®) for the treatment of opioid use disorder**

STUDY ID 843403

PROTOCOL VERSION V5.0

I have read the referenced protocol. I agree to conduct the study in accordance to this protocol, in compliance with the Declaration of Helsinki, Good Clinical Practices (GCP), and all applicable regulatory requirements and guidelines.

Principal Investigator Name	[name]	Signature
Affiliation:	University of Pennsylvania	Date 7/17/2023

END OF DOCUMENT

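### Section 7.2 lets randomised but uninjected participants be replaced, although Section 9.1 counts refusal and dropout as treatment failure; the losses this hides may differ by arm

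*Combined protocol and SAP*

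**What the plan says.** - **Replacement (Section 7.2).** "Subjects who sign the informed consent form and are randomized but do not receive the injection may be replaced". The next sentence bars replacement once the injection has been given. There is no criterion, cap or reporting rule, and no statement of how a replacement is allocated.
- **Outcome (Section 9.1).** Treatment failure includes "or refusing XRNTX or XRBUP, or dropping out of study entirely". The Phase 2 text in the same section repeats this.
- **Exclusion (Section 2.3.1).** People who cannot complete detoxification or induction leave the study and are referred elsewhere.
- **Analysis population (Section 9.3).** The only population defined is randomised participants with at least one dose of study drug.
- **Timing (Section 6.1).** "we will detoxify all participants to abstinence and randomize after abstinence from illicit opioids has been achieved"; then "The induction to XRNTX or XRBUP will commence immediately after the baseline MRI session". The Schedule of Activities instead has a column headed "Screening detox and randomization (Day -14".
- **Route to the first injection.** For XRNTX: "The XRNTX participants will receive 50 mg of oral naltrexone for 7-10 days after detoxification followed by the 1st XRNTX". For XRBUP, Section 2.3.1 describes induction "by injection of one or more weekly XRBUP in 8mg, 16mg or 24 mg strength". Section 2.3.1 also asks for a negative naloxone challenge for XRNTX and says that XRBUP does not need one.
- **Eligibility (Section 5.1).** "Interested in injectable extended release agonist or antagonist treatment".

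**The concern.** Randomisation protects a comparison as long as each person, once allocated, stays in the arm and is counted there. Here the allocation is evident: the synopsis title and Sections 3.1 and 4.2 call the trial open label. Section 4.1 says single-blind, but the arms differ visibly in route and schedule. A participant who learns the arm and declines it, or who does not get through induction, is a failure under Section 9.1, replaceable under Section 7.2, excluded under Section 2.3.1 and possibly outside the analysis set under Section 9.3. Nothing says which rule prevails.

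The comparison of XRNTX with XRBUP is the purpose of the trial, and Section 2.3.1 detoxifies everyone specifically to avoid selection between the arms. If early failures are removed more often from one arm, that selection returns after allocation, and the treatment-failure comparison is between people who accepted and tolerated the start of their drug.

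**Working it through.** No figure in the plan measures this, so there is none to reproduce. The check compares the rules and then gives an illustration on stated assumptions.

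**1. What happens to one person.** Take a participant randomised after abstinence who then refuses the assigned drug before any dose.
- Section 9.1: treatment failure.
- Section 7.2: may be replaced.
- Section 9.3: no dose, so outside the analysis population.
- Section 3.2: the adherence endpoint takes values 1, 2 or 3, so there is no value for this person.

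Now take an XRNTX participant who takes oral naltrexone and stops before the injection. Section 7.2 allows replacement because no injection was given. Section 9.3 may still include the person if oral naltrexone counts as study drug, which is not stated. Replaced and replacement could then both be analysed.

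**2. Is the route to injection the same in both arms?** No. XRNTX alone has the naloxone challenge and the 7-10 days of oral naltrexone. If only XRNTX participants take the challenge, it must follow allocation.

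**3. What is the injection in Section 7.2?** It is not defined.
- If any study injection counts, XRBUP participants pass the replacement limit at their first weekly injection, early in induction, and XRNTX participants pass it 7-10 days into theirs.
- If it means the first monthly injection, Section 6.1 says the two cohorts are meant to be synchronised, and the timing difference largely disappears. The conflict in step 1 and the arm-specific hurdles in step 2 remain.

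**4. Can the size be derived?** No. Section 5.3 expects about 75% of 200 to reach the first monthly injection and gives the result as 160, whereas 0.75 × 200 = 150. It ties that loss to achieving abstinence, which Section 6.1 places before randomisation. Neither figure gives loss after randomisation, and neither is split by arm.

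**5. Illustration.** Assumptions, not plan figures: 5% not injected in XRBUP; 5%, 10%, 20% or 30% in XRNTX; failure risk f = 40% among the injected in both arms; every uninjected person a failure, as Section 9.1 says. The target of 80 per arm is taken from Section 9.2. With q the proportion not injected:
- number randomised = 80/(1 − q)
- failure among all randomised = q + (1 − q) × f

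XRBUP: 80/0.95 = 84 randomised, 4 replaced; failure 0.05 + 0.95 × 0.40 = 43%.

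| XRNTX not injected | XRNTX randomised | XRNTX replaced | XRNTX failure, all randomised | Difference from XRBUP | Failure among injected, both arms |
|---|---|---|---|---|---|
| 5% | 84 | 4 | 43% | 0 points | 40% |
| 10% | 89 | 9 | 46% | 3 points | 40% |
| 20% | 100 | 20 | 52% | 9 points | 40% |
| 30% | 114 | 34 | 58% | 15 points | 40% |

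With equal non-injection there is no distortion between arms. If XRBUP lost more, the sign would reverse. The last column applies whether or not anyone is replaced, so amending Section 7.2 alone would not recover the difference; the analysis set must change too.

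**The case against.** The strongest reply is that Section 7.2 probably means the first monthly injection. The Schedule of Activities separates induction (day 0-10) from Injection 1 (day 10), Section 6.4 counts observed injections on days 10 and 40, and Section 6.1 intends the monthly starts to coincide. On that reading both arms are replaceable for essentially the same time. This stands, and the point does not rest on unequal windows.

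Three stronger readings are tempting, and the documents do not support them.
- A reader might infer that XRBUP allocations are fixed at once and cannot be swapped. An XRBUP participant who refuses before any injection is replaceable too.
- A reader might infer that a replacement takes over the vacated assignment, so that recruiters know the next arm. Sections 6.3 and 7.2 are silent on this. Section 6.3 describes an urn managed off site, away from staff who work with participants, with access to one subject at a time.
- A reader might take the shortfall in Section 5.3 as the number replaced. It is tied to abstinence, which Section 6.1 places before randomisation. The Schedule of Activities groups randomisation with detoxification, which leaves the timing unsettled but supplies no count.

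It can also be said that eligibility of people who want only one drug is inferred from the word or, and that the consent form, not available here, may require acceptance of either arm. That is fair. The criteria themselves contain no such requirement.

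**Conclusion.** The point holds as an unresolved conflict between rules: replacement, exclusion and an all-treated population on one side, and a failure definition that includes refusal and dropout on the other. Because XRNTX has extra steps before its first injection, the losses may be unequal by arm. This is a possibility created by the rules, not a demonstrated bias.

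Size and direction cannot be derived from the documents. The 3-15 point range rests wholly on the assumed non-injection rates and the assumed equal 40% failure among the injected, and it would be zero with equal non-injection.

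The conclusion concerns the treatment-failure outcome. A person who is never injected would ordinarily have no on-treatment scan, replaced or not, so the imaging contrast stays restricted to those who start treatment, and reporting non-injection by arm is what lets a reader judge it. The change should be made in the next amendment.

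**What to change.** 1. **Section 7.2.** State that randomised participants are not replaced in the analysis. They keep their assigned arm and count in it for the treatment-failure outcome, with refusal or failed induction scored as failure, in line with Section 9.1. Define the injection.
2. **Sections 2.3.1 and 9.3.** Reconcile both with this. Leaving study treatment need not mean leaving the analysis. Add an all-randomised population for the treatment-failure outcome, and say whether oral naltrexone counts as a dose of study drug.
3. **Reporting.** Give the number not injected, with reasons, by arm.
4. **Further recruitment.** If recruitment continues to reach a target, each new participant gets a fresh urn draw within the sex stratum.
5. **Sections 5 and 5.1.** Require willingness to receive either XRBUP or XRNTX as assigned.
6. **Timing and blinding.** Reconcile Section 6.1 with the Schedule of Activities on when randomisation occurs, and Sections 4.1 and 6.3 with the open-label description.

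The cost is wording in several sections rather than one. A few candidates who would take only one drug will not be enrolled, and failure rates may look less favourable because early refusals and failed inductions are counted.
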